## 10.3 Follow-up Data

Participants will be followed-up for a total of 12 months. Follow up data collection will be collected at 3 months, 6 months, 9 months and 12 months post-randomisation for both groups, which will be conducted as per baseline assessment. Participants will be actively contacted via telephone call by the MR researcher for up to 3 weeks post-data collection appointment schedule to complete the follow-up data collection. Participants will be contacted a maximum of 3 times over the 3 week period, with voicemails being left providing a contact number should the participant wish to discuss the trial or CRF. The MR researchers will record missed

appointments, as well as how many times they have been contacted (by text, telephone or via case provider) to arrange follow-ups.

# 10.4 Data collection schedule

Data	Time point collected				
	Baseline	Month 3	Month 6	Month 9	Month 12
Eligibility form (includes SMI diagnosis)	х				
Contact details	х				
Consent	х				
Demographic details and sexual health history	х				
**					
Non-volitional sex *	х				
SERBAS *	х	х	х	х	х
HIV-KQ **	х	х	х	х	х
Motivation to Engage in Safer Sex **	х	х	х	х	х
Condom use Self-Efficacy Scale **	х	х	х	х	х
Behavioural Intentions for Safer Sex **	х	х	х	х	х
General questions about sexual health: items	х	х	х	х	х
adapted from NATSAL 3**					
ED-5D-5L *	х	х	х	х	х
ReQol **	х	х	х	х	х
Health care resource use *	х	х	х	х	х
Qualitative interview			х		
Adverse event reporting	Ongoing				
Change of status reporting	Ongoing				

\* Collected as part of the MR researcher interview CRF. The primary outcome (SERBAS) will be the first measure collected in this CRF.

# 11. Study treatments

Participants will be randomised to either receive the intervention plus usual care or usual care only.

moreRESPECT\_Protocol

IRAS ID: 309345

REC Reference: 23/NW/0157

\*\*Collected as part of the participant self-completed CRF

11.1 Sexual Health Intervention

University for the Common Good

The sexual health intervention was designed and developed during the RESPECT feasibility study (18). It comprises of three components:

- 1) Raising awareness of issues related to sexual health such as contraception choices, how to engage in sex acts safely, positive intimate relationships (Information)
- 2) Facilitating dialogue and reflection on own (and sexual partners) sexual health and unmet needs for advice, treatment, testing, contraception, skills (Motivation)
- 3) Behavioural skills (such as how to use a condom correctly), negotiate safer sex and/or communicate preferences or boundaries effectively (Behaviour)

The intervention manual is divided into sections on a variety of topics and includes interactive exercises rather than didactic presentation of information. There is flexibility to focus on people's specific needs and interests, sexuality and gender identity.

*Timing:* It will be delivered over 3 x one-hour 1:1 sessions by a person from the local NHS service (interventionist) who has received specific training from the study team. The three intervention sessions should be delivered as soon as practical after randomisation but must be completed before the 3-month follow-up data collection time point.

Location: It is designed to be delivered face to face or using remote videoconferencing sessions. In the feasibility study it was delivered in a person's home or using an office in a local service, and this was found to be acceptable to participants. The intervention can also be delivered on inpatient mental health units if a patient is awaiting discharge but remain in inpatient care due to the unavailability of suitable community placement.

Interventionist: An Intervention lead will work with the NHS sites to provide training and supervision for those who will be delivering the intervention. The criteria for the interventionists are broad:

- · Experience of working with people who live with SMI
- Comfortable talking about sexual health and sexual practices
- Ability to work in a non-judgemental way, using core skills of engagement, empathy, listening, reflecting and summarising. Each recruiting site will be required to provide interventionists with protected time to deliver the intervention to participants in the NHS organisation (3 x one-hour sessions per participant).

The person does not require prior expertise of working in sexual health.

Fidelity to the manual: This will be assessed by a brief checklist at the end of each session completed by the interventionist. The interventionist will check off which of the session's components have been completed, which were omitted and why, and note any specific issues or needs that arose and if they were addressed in the session. The interventionist will also record the date and timing of each session and whether there were any cancellations and rearrangements. This data will be sent to the YTU for storage.

*Engagement:* Reminders will be sent by the interventionist via the participant's preferred communication method (e.g. such as text or telephone calls).

*Training and supervision*: Intervention training will be provided by the Intervention Lead based at Glasgow Caledonian University, along with the Lived Experience Advisory Group (LEAG) and will introduce staff to the key-concepts and procedures involved in the intervention and research. The training will follow a similar format to the RESPECT feasibility study and will comprise of the following:

- 1) Introduction to the study including learning from the feasibility study.
- 2) Overview of the diverse sexual health needs that people with SMI experience.
- 3) Induction to the intervention. Each component of the manual will be presented as well as discussions about how to deliver the content to a range of people. Interventionists will practise using the materials to build confidence.

All interventionists will have access to additional resources should they be required - e.g., specific needs of people who identify as Lesbian, Gay, Bisexual, Transgender, Queer (LGBTQ).

Suitable interventionists from each NHS organisation will be identified in the months before the trial opens to recruitment and will be required to complete the one day of intervention training. This will be delivered online. This will be a rolling programme (repeated approximately every 2 months) to ensure that the intervention pool can be refreshed should sites lose interventionists,

and to allow for the staggered opening of sites. During the intervention delivery period the interventionists will have access to online monthly supervision sessions with the intervention lead.

## 11.2 Usual Care

There is no specific service for people with SMI in terms of their sexual health. All participants (irrespective of allocation) will continue to receive usual care for mental health and sexual health. All participants will all be given a localised sexual health services leaflet developed for the study (containing names and contact details of local sexual health, family planning and domestic violence support services) and sample pack of condoms.

# 12. Internal pilot

The first eight months will be run as an internal pilot with three progress measures used to determine the continuation of the trial: recruitment, attendance at sessions, and response rate at 3 months.

	GREEN	AMBER	RED
	{progress without any	{progression may be	{consider stopping the
	major modifications}	possible with	trial}
		modifications}	
Pilot target recruitment	100% or more (n>=80	Between 75% and 99%	<75% (n<60
	participants)	(n=60-79 participants)	participants)
Attendance at	Average of 75-100%	Average of 50-74%	Average of <50%
intervention (sessions	attendance	attendance	attendance
attended)			
Questionnaire response	75-100%	50-74%	<50%
rate at 3 months			

# 13. Participant incentives

In acknowledgment of the time involved and as a thank you, each participant will receive a £10 voucher each time they complete and return a self-completed questionnaire (baseline, 3, 6, 9 and 12 months) up to a maximum of five vouchers in total, per participant.

## 14. Completeness of data

The primary outcome will be collected via meetings with the MR researcher (face to face or remotely) and therefore we expected minimal missing data, with the exception of those participants who do not attend/engage with appointments or whom MR researchers are unable to locate. Furthermore, the return of data is incentivised with a voucher, and therefore we believe participants will be motivated to complete and return data. We also know that there was good completeness of data in the RESPECT feasibility study with excellent engagement with data collection appointments by both intervention and control group. In addition, the participants reported that they found the data collection comfortable and interesting and appreciated receiving a Love to Shop Voucher (19).

#### 15. Data handling, management and storage

Information with regards to the study participants will be kept confidential and managed in accordance with the Data Protection Act, NHS Caldicott Guardian, UK Policy Framework for Health and Social Care Research and the Health Research Authority.

Data management will ensure that each site and study participant is assigned a unique trial identification number at the start of data collection; all data (paper and electronic) will use this unique trial identification number. A record sheet linking patient identity, contact details and trial identification number for all participants will be kept at each site. This will be placed securely in a locked filling cabinet, separate from datasheets.

moreRESPECT\_Protocol

IRAS ID: 309345

REC Reference: 23/NW/0157

Identifiable data of consenting participants will be stored on paper and on a secure password protected electronic server at the University of York, for the purposes of assisting in follow-ups during the study. Personal data will be stored separately to the trial data. Study data will be collected using anonymous paper CRFs, which will be completed by both the MR researcher and the participant and returned to YTU via post. Paper CRFs collected from participants will be kept in a safe, secure environment (locked drawer in a locked office) by the MR researchers and posted as soon as possible to the YTU. Analytical datasets will not contain any identifiable information. The data management system, CRFs, identifiable data and non-identifiable data will be stored securely for up to 10 years after the end of the trial and then destroyed securely in accordance with the current YTU Standard Operating Procedures. Consent forms will be stored up to 6 years after the end of the trial and then destroyed, as allowed by the Prescriptions and Limitations Act.

All data will be kept secure at all times, maintained in accordance with the requirements of GDPR and archived according to Good Clinical Practice (GCP) regulations. Paper data collection forms transferred to or from the YTU will be coded with a participant ID. Data will be held securely on paper and electronically at YTU and appropriate processes put in place for the transfer, storage, restricted access, and disposal of personal information. Relevant Standard Operating Procedures (SOPs), guidelines, and work instructions in relation to data management, processing, and analysis of data will be followed.

Participating sites will be expected to maintain a file of essential trial documentation (Investigator Site File), which will be provided by YTU, and keep copies of all completed paper assessment packs and consent forms for the trial securely (until these are returned to YTU).

In terms of the qualitative data, this will be collected using Microsoft Teams at Glasgow Caledonian University. Interviews will be conducted with participants and recorded in Teams. This generates a transcript and an MP4 file. This will be stored in a secure drive at Glasgow Caledonian University. The transcript will be cleaned and de-identified and the names removed and the participant will only be identified by their unique trial ID number. Any personal information required will also be coded with this identification number and kept in a password protected electronic file or separate filing cabinet which will be locked at all times. Any quotes published will be anonymous further protecting participant confidentiality. All qualitative data will be stored and analysed using a secure drive at Glasgow Caledonian University. The qualitative data will be stored for 10 years.

moreRESPECT\_Protocol

IRAS ID: 309345

REC Reference: 23/NW/0157

All data from the trial will be collected using paper-based CRFs. These will be filled in by both the researchers and the participants themselves. MR researchers and clinicians will be responsible for ensuring the completeness and reliability of the data from their site, and then for securely transferring this data to YTU. Once the paper forms have been returned to YTU, this data will be entered into a master database for the trial using either optical scanning techniques or will be entered manually.

## 16. Qualitative research

## 16.1 Interview format

The aim of the qualitative interviews is to gather richer data about what works for whom under what circumstances with regards to sexual health in this group (realist evaluation). We will purposively sample people from those who consented to participate in the trial and consented to be considered for the qualitative interviews at 6 months post randomisation. The sampling framework will ensure there is representation across a range of diversity characteristics including location, sexuality, gender, ethnicity, age, and type of mental health condition.

Sample Size: In qualitative research, the sample size is not precise, and it is more important to achieve a range of diverse participants. We will aim to interview up to 40 people via videoconferencing (MS Teams) or telephone. The interviews will be conducted by peer researchers who are part of the LEAG, and the MR researcher based at Glasgow Caledonian University. The peer researchers will be employed as casual workers at Glasgow Caledonian University, receive supervision and training from the chief investigator (CI) (who is experienced in realist interviews and evaluation). All have conducted GCP training, and will have letters of access from relevant NHS sites. In addition, the peer researchers will co-produce the topic guide and will receive training and practice in undertaking the realist interview.

The interviews will take approximately 40-60 minutes. It will be based on realist evaluation and will seek to test and refine a set of programme theories about what works in terms of addressing sexual health needs for people with severe mental illness.

moreRESPECT\_Protocol

IRAS ID: 309345

REC Reference: 23/NW/0157

The data obtained will complement the trial data and identify the contexts, mechanisms that lead to positive outcomes in the trial by comparing those who had participated in the intervention as well as those in the control group, as well as across different sites and locations.

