#### **PLAIN ENGLISH SUMMARY**

People with severe mental illness (SMI) have significant needs in terms of physical health compared to the general population. Initiatives have commenced to address this; however, sexual health has been missed off the agenda. Like everyone else, positive sexual relationships are important for people with SMI, but this is rarely discussed in routine mental health care. Therefore, they can be unaware of important information such as where to get sexual health advice, how to reduce risk of sexually transmitted infections, contraceptive choices and finding relationships that are mutually respectful, not violent or abusive.

In a National Institute for Health and Care Research (NIHR)-funded feasibility study, this research team developed a 3-session support package that helped people with SMI to think about their own sexual health and provided useful information about how to improve their sexual health. Following the success of the feasibility study, this full trial will examine the effectiveness and cost-effectiveness of the intervention by recruiting 400 people with SMI from National Health Service (NHS) community mental health teams across England and Scotland.

People who agree to take part will be randomly allocated to either usual care (control arm) or usual care plus the moreRESPECT intervention (intervention arm). Data will be collected at baseline and then at 3-, 6-, 9- and 12 months post-randomisation. As part of a nested process evaluation, interviews with a small group of participants will also be conducted at 6 months post randomisation to find out how they found the support package and whether it worked better for some than others and in what circumstances.

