# 1.3 Researcher titles, roles and responsibilities

Researcher title:	Based at:	Responsibility:	Access to data:	Blinded to participant
				allocation:
moreRESPECT researcher	Site or University employed	
 
Promote study in public areas of NHS sites such as waiting rooms, communal areas, with prior permission of clinical team
 
Speak to potential participants patients who have given consent to be contacted,
 
Obtain informed consent
 
Conduct baseline and follow-up assessments
 
Complete the MR Researcher interview CRF including the SERBAS questionnaire
 
(if in clinic) confirm completion of the Participant self-completed CRF
 
Post completed CRFs to YTU
 
Conduct reminder telephone calls with participants who have not completed their CRF
 
Complete change of status and AE forms and notify YTU
 
	- Consent form and consent to contact forms - Participant CRFs - Patient identifiable data	Yes
R&D staff	Site	
 
Promote study in public areas of NHS sites such as waiting rooms, communal areas, with prior permission of clinical team Maintain and update a record sheet of patients enrolled at site
 
Post completed CRFs to YTU
 
Maintain a file of essential trial documentation
 
	
 
Participant allocation
 
Consent form and consent to contact forms
 
Participant CRFs
 
Patient identifiable data
 
	No
YTU staff  moreRESPECT Pro	YTU	
 
Conduct randomisations
 
Inform participant, sites, MR researcher, lead interventionist (if applicable), participants GP and participants NHS care provider of participant randomisation
 
Support day to day trial management and monitoring activities
 
Conduct site set-up
 
 RAS ID: 309345 REC Reference: 23/NW/02	- Participant allocation - Consent form and consent to contact forms - Participant CRFs - Patient identifiable data	No

moreRESPECT\_Protocol

IRAS ID: 309345

REC Reference: 23/NW/0157

		Provide trial Standard Operating     Procedures     File, process and analyse patient and researcher data		

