telephone call, the University of York's secure Drop-off system or via providing access to the secure Trial Management System. The intervention coordinator/lead will assign an interventionist to the participant and will confirm to YTU who this is; YTU can then add this information to the participants details. The interventionist will keep a record of intervention appointments and attendance by ID number. This will be stored securely until the intervention is completed, and then it will be transferred to the YTU.

The MR researchers who will be collecting follow-up data will be blinded to the participants' allocation. Participants will be asked not to reveal if they had the intervention or not and any accidental revelation of the trial arm will be recorded by the MR researcher as unblinded. Those who deliver the intervention will know the allocation but will not communicate this to the MR researchers working on the study. The trial statisticians and the health economist will not be blinded to allocation.

The participants GP and NHS Care Provider will be informed about their patients' study participation via letter generated from the trial management system; however, they will not be informed about allocation status, reducing the risk of inducing behaviour change based on this knowledge. However, allocation may be revealed to a participant's GP and NHS Care Provider in response to an adverse health event if necessary.

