# 19.3 Withdrawal/dropout of participants

Participants may withdraw from the study at any time without influencing their future care or treatment. Withdrawal may refer to the following situations:

- 'Withdrawal from intervention': where a participant wishes to withdraw from the study intervention, but is prepared to continue completing follow-up questionnaires (i.e. no intervention sessions are attended but the data is still collected). This is pertinent only to the sexual health intervention arm of the study.
- 'Withdrawal from follow-up': where a participant wishes to withdraw from completing any further follow-up interviews after completing their intervention sessions or after baseline data collection if in the control group.
- 'Full withdrawal': where a participant wishes to withdraw from both the study intervention (if applicable) AND from completing any further follow-up interviews.
   Where full withdrawal is requested this will be termed trial exit, where a participant leaves the trial and no further data are collected from them.

A participant can be withdrawn without their consent from the intervention and/or the trial for reasons of risk or harm to self and/or others. This would only be actioned with evidence of serious and significant risk. In these instances, a safeguarding protocol developed for the trial will guide the interventionist and/or researcher in the appropriate action to be taken in conjunction with the lead research clinician and the duty worker in the organisation. Where possible this would include discussion with the participant so that they understood the reason for discontinuing their participation, however would not be an essential requirement.

Where participants lose capacity to consent during their time in the study, they will be withdrawn from further follow up; however, data collected until this point will be retained for use. No further data would be collected or any other research procedures conducted in relation to the participant.

We will ensure that the moreRESPECT researchers are aware of the differences in types of withdrawal, and that they are explicit about whether participants wish to withdraw from the intervention, follow up, or both. In any event, a change of status form will be completed and YTU will be informed.

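### One researcher role is both the blinded SERBAS assessor and a party to arm-revealing tasks (6-month qualitative interviews, recording withdrawal from the intervention), with no stated separation for the same participant

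*Protocol*

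**What the plan says.** Protocol section 1.3 makes the MR researcher the primary outcome assessor, with the task "Complete the MR Researcher interview CRF including the SERBAS questionnaire", and marks the whole role as blinded. Section 8.4 repeats this: "The MR researchers who will be collecting follow-up data will be blinded to the participants' allocation". It supports the promise in several ways: YTU writes to participants with their allocation, participants are asked not to disclose it, interventionists do not pass it on, and any accidental disclosure is logged.

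Two other parts of the protocol give the same role work that reveals the arm.

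- **Qualitative interviews.** Section 16.1: "The interviews will be conducted by peer researchers who are part of the LEAG, and the MR researcher based at Glasgow Caledonian University". The plain English summary gives timing and content: "interviews with a small group of participants will also be conducted at 6 months post randomisation to find out how they found the support package". Section 16.1 adds that intervention and control participants will be compared.
- **Withdrawal.** Section 1.3 gives the MR researcher the task "Complete change of status and AE forms and notify YTU". Section 19.3 requires MR researchers to be "explicit about whether participants wish to withdraw from the intervention, follow up, or both". The same section says that withdrawal from the intervention applies to the intervention arm only and that such participants continue to give follow-up data.

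**The concern.** The primary outcome is a count of private behaviour, obtained in a semi-structured interview with people who know their allocation. Participant blinding is not available, so a blinded assessor is the remaining guard against probing or recording the two arms differently. An interview about the support package cannot leave the interviewer unaware of whether the participant received it. A form saying that someone has left the intervention identifies the arm with certainty.

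If the same researcher later takes that participant's SERBAS, the assessment is not blinded, and this results from the plan and not from an accident. The log in section 8.4 is written for accidental disclosure, so it would not clearly capture these cases. The trial could then not report blinded outcome assessment without qualification.

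**Working it through.** The protocol gives no figure on this point, so there is none to reproduce. The sample size, alpha and power do not depend on it.

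**Do the tasks meet in one role?**

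1. Section 1.3 marks the MR researcher role as blinded without exception and describes its holders as employed by a site or a university. The interviewing MR researcher at the sponsor university falls within that description.
2. Section 8.3 allows remote data collection, and section 10.3 conducts follow-up in the same way. Location therefore does not separate the interviewer from the assessor.
3. No section says that the interviewing researcher, or the one who completes a change of status form, takes no later SERBAS from that participant.
4. Under section 11.1 the sessions must finish before the 3-month data collection. Withdrawal from the intervention can therefore become known before any of the four follow-up assessments.

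**Reach of the interview route.** Inputs: up to 40 interviews (section 16.1), 400 participants (section 9), four assessments at 3, 6, 9 and 12 months (section 10.1).

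- Participants: 40 / 400 = 10%.
- Scheduled assessments: 400 × 4 = 1,600.
- Interview after the 6-month SERBAS: 40 × 2 = 80, and 80 / 1,600 = 5%.
- Interview before the 6-month SERBAS: 40 × 3 = 120, and 120 / 1,600 = 7.5%.

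These are upper limits. They suppose that the MR researcher does every interview and then takes every later SERBAS from those people.

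**Illustrative effect on the rate ratio.** Assumptions, none of them in the protocol: interviewed participants have average counts, spread evenly over the four windows; an unblinded assessor under-records by a proportion x in intervention participants; control counts are recorded correctly. With 1:1 allocation there are 200 per arm. If k intervention participants are interviewed, the rate ratio is multiplied by 1 − (k/200) × (2/4) × x.

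| k | x = 10% | x = 50% |
|---|---|---|
| 20 (half of the interviews) | 1 − 0.10 × 0.5 × 0.10 = 0.995 | 1 − 0.10 × 0.5 × 0.50 = 0.975 |
| 40 (all of the interviews) | 1 − 0.20 × 0.5 × 0.10 = 0.990 | 1 − 0.20 × 0.5 × 0.50 = 0.950 |

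If three windows are affected, the 10% column becomes 0.9925 and 0.985.

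The design targets a rate ratio of 30/40 = 0.75. On the log scale, 0.995 is ln(0.995)/ln(0.75) = 1.7% of that effect, and 0.990 is ln(0.990)/ln(0.75) = 3.5%.

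**Withdrawal route.** No withdrawal rate is given, so the total cannot be sized. Under the same assumptions and x = 10%, one participant unblinded before all four assessments contributes up to (1/200) × 0.10 = 0.0005. Twenty such participants would contribute 0.01, the same as 40 interviewed intervention participants.

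**The case against.** The case for leaving the text alone has four parts.

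- **One person, and shared work.** Section 16.1 names a single MR researcher, who shares the interviews with peer researchers and is nowhere said to be the interviewees' assessor. Section 8.4 blinds those who collect follow-up data, which may leave room for an MR researcher who does not. This stands as a limit on size. It does not remove the conflict, because section 1.3 marks the whole role as blinded and no section separates the tasks.
- **Most withdrawals do no harm.** Full withdrawal and withdrawal from follow-up leave no later SERBAS to bias. This is right. Only withdrawal from the intervention matters here.
- **There are other safeguards.** YTU letters, the request for silence and the log are real protections. The log, however, is limited to accidental disclosure.
- **Participants are unblinded and report the outcome themselves.** Assessor blinding therefore gives only partial protection. This stands, but it is no reason to give up the part that can be kept.

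A reader might also infer from the YTU row of section 1.3, "Inform participant, sites, MR researcher, lead interventionist (if applicable), participants GP and participants NHS care provider of participant randomisation", that MR researchers are told the arm of every participant. The protocol does not support this. The same list includes the GP and the care provider, who under section 8.4 are not told the allocation. The data-access column of the role table lists allocation for R&D staff, YTU, the intervention lead and the interventionist, but not for the MR researcher. Section 8.4 also has YTU inform the participant expressly to keep the MR researcher blinded. The line most naturally means the fact of randomisation and is a wording ambiguity only.

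**Conclusion.** The inconsistency is real and limited in reach. The protocol promises blinded SERBAS assessors and gives the same role two tasks that reveal the arm, without keeping them apart from later assessments of the same participant. Through the interviews this reaches at most 10% of participants and 5% to 7.5% of scheduled assessments. Through withdrawal forms it reaches an unknown number, all in the intervention arm, possibly before any follow-up assessment.

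With an assumed 10% under-recording, the interview route moves the rate ratio by about 0.5% to 1%, depending on how many interviewees are in the intervention arm. That is small against a targeted 25% reduction, and it rests on assumptions the documents neither give nor exclude. It would be wrong to conclude that assessor blinding fails across the trial or that half of all outcome data are affected. This should be fixed because the contradiction lies in the protocol itself and is easy to remove, not because the expected bias is large.

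**What to change.** - **Section 16.1:** state that whoever conducts a participant's qualitative interview collects no later SERBAS from that participant, or that the peer researchers do the interviews. Keep the interviews at 6 months, since moving them would change the planned process evaluation.
- **Sections 19.3 and 1.3:** have withdrawal from the intervention taken and recorded by the interventionist or YTU, with the MR researcher recording only withdrawal from follow-up. The interventionist already keeps the attendance record under section 8.4. If a participant volunteers such a withdrawal to the MR researcher, log it as unblinding under section 8.4.
- **Section 1.3, YTU row:** as a clarification only, say that the MR researcher, GP and care provider are told that the participant has been randomised, not to which arm.

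The cost is a wording amendment and the reassignment of existing tasks, with no extra staff. The drawback is slightly less flexible scheduling of interviews and follow-up visits.
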